### Vital Signs Summaries:

- Vital signs and change from baseline
- Markedly abnormal vital signs

### Vital Signs Listings:

- Vital Signs
- Markedly abnormal vital signs

#### **4.6.3.5. Columbia-Suicide Severity Rating Scale**

Both Screening/Baseline Version of Columbia-Suicide Severity Rating Scale (C-SSRS) and Since Last Visit Version of C-SSRS will be summarized and listed for all applicable parameters.

#### **4.6.3.6. Questionnaire for Impulsive-Compulsive Disorders in Parkinson's Disease Rating Scale**

Questionnaire for Impulsive-Compulsive Disorders in Parkinson's Disease Rating Scale (QUIP-RS) conducted at Baseline and Week 17 will be summarized at each visit for 4 ICDs (gambling, sex, buying, and eating), 3 related disorders (hobbyism, punding, and medication use), as well as the total QUIP-RS score. Higher scores signify a higher magnitude of the impact of impulse control disorders.

A listing will be created for all individual questions as well as summary scores of 4 ICDs, 3 related disorders and the total score.

#### **4.6.3.7. Electrocardiograms**

A standard 12-lead electrocardiogram (ECG) will be assessed to measure PR, QRS, QT, QTcB and QTcF intervals, as well as overall assessment of ECG.

##### **Derivations and Definitions:**

Markedly abnormal ECG will be classified per categories below:

Observed value for QT, QTcB and QTcF intervals:

- > 450 msec
- > 480 msec
- > 500 msec

Observed change from baseline for QT, QTcB and QTcF intervals:

- > 30 msec increase from baseline
- > 60 msec increase from baseline

##### **ECG Summaries:**

- Observed and change from baseline for all ECG parameters
- Markedly abnormal ECG findings

##### **ECG Listings:**

- ECG results including ECG interpretation
- Markedly abnormal ECG findings

## 4.7. Other Analyses

All other analyses, summaries, listings will use the Safety Analysis Set unless otherwise specified.

### 4.7.1. Participant Enrollment, Study Disposition

Enrollment disposition will use the Enrolled Analysis Set to summarize the number of participants who signed informed consent, the number of participants who screen failed with corresponding inclusion/exclusion criteria, and the number of participants randomized.

Study disposition will use the Full Analysis Set to summarize participants who received at least one dose of study treatment, who completed the study, and who discontinued study treatment early along with the primary reason for discontinuation. In addition, similar disposition summaries for both DTOP (Weeks 1 to 5) and MTP (Weeks 5 to 17) will be provided.

Number of participants by country and site will be summarized.

Participant disposition details based on the Enrolled Analysis Set will also be listed to at least contain basic demographic information, inclusion in the analysis sets (Full, Safety, mITT [REDACTED]), date of informed consent and date of randomization, planned/actual treatment arms, first/last dose of study treatment, study completion status and primary reason for discontinuation.

Study eligibility criteria will be listed for all study participants based on the Enrolled Analysis Set.

Participants who receive study intervention different from the randomized treatment will be listed.

### 4.7.2. Analysis Sets

#### Analysis Sets Summaries:

- Number and percentages of participants in the Full, Safety, mITT [REDACTED] Analysis Set will be summarized using the Enrolled Analysis Set.

#### Analysis Sets Listings:

- Participant level inclusion for each analysis set will be listed by the disposition listing defined in Section 4.7.1.

### 4.7.3. Protocol Deviations

#### Definitions and Derivations:

Reported protocol deviations will be classified as “Important” and “Non-important” categories for this study and managed according to the protocol deviation plan.

A participant with more than one protocol deviation reported under the same protocol deviation type and subtype will be only counted once in the protocol deviation summaries, yet each protocol deviation will be listed separately.

#### Protocol Deviation Summaries:

- Summary of Protocol Deviations excluding COVID-19 related deviations (Safety Analysis Set, and FAS)
- Summary of study visits and assessments impacted due to COVID related reasons (Safety Analysis Set, and FAS)
- Summary of Important Protocol Deviations (IPDs) (Safety Analysis Set, and FAS)

**Protocol Deviation Listings:**

- Listing of reported protocol deviations

**4.7.4. Demographic and Baseline Characteristics**

Demographic and baseline characteristics including race, ethnicity, sex at birth, age, height at screening, weight, body mass index (BMI), female with childbearing potential, baseline TETRAS ADL component score (sum of items 1 to 11, unmodified), baseline TETRAS PS component score (sum of items 6a, 6b and 7, unmodified), baseline TETRAS composite outcome score, baseline TETRAS composite outcome score stratification ( $\leq 17$ ,  $> 17$ ), baseline CGI-S and PGI-S categories and baseline MDS-UPDRS tremor score (sum of items 2.10, 3.15, 3.16, 3.17 and 3.18) will be summarized by treatment group for the Safety, FAS [REDACTED] Analysis Sets.

A concordance analysis using Cohen's kappa will be conducted using the Full Analysis Set to examine the agreement of the classification of participants into randomization strata using different data sources, i.e., the IRT vs the derived baseline TETRAS composite outcome score stratification ( $\leq 17$ ,  $> 17$ ).

The following provides the example SAS code for the Cohen's kappa analysis:

```
PROC FREQ;
  TABLE IRT*DERIVED_TETRA / AGREE;
  RUN;
```

**Demographic and Baseline Characteristics Summaries:**

- Summary of demographic and baseline characteristics (Safety, FAS [REDACTED] Analysis Sets)

**Demographic and Baseline Characteristics Listings:**

- Listing of demographic and baseline characteristics

**4.7.5. Medical History**

Medical conditions collected on the Medical History page of the CRF will be coded by SOC, PT using MedDRA version 27.0. Participants with multiple medical conditions under the same SOC and PT will only be counted once in summaries.

The PD history collected on 'PD-Specific Disease History' eCRF page will be summarized for key disease characteristics including elapsed time since the date of PD symptom onset, elapsed time since the date of tremor onset, elapsed time since the date of PD diagnosis, family history of PD, H&Y stage, and presence of On and Off periods.

"On" and "Off" periods are symptom fluctuations that can occur in people with Parkinson's disease. On periods: When Parkinson's medications are working well, and symptoms are less noticeable. Off periods: When Parkinson's medications wear off, and symptoms return or worsen.

#### **Medical History Summaries:**

- Summary of medical history by SOC and PT
- Summary of PD-specific disease history

#### **Medical History Listings:**

- Listing of medical history
- Listing of PD-specific disease history

#### **4.7.6. Prior and Concomitant Medications**

##### **Derivations and Definitions:**

Prior and concomitant medications will be coded to ATC level 4 and preferred drug name using WHO Drug Dictionary Version March 2024, and will be classified as follows:

Prior medication is defined as any medication started prior to the first dose of study treatment.

Concomitant medication is defined as any medication started prior to the first dose of study intervention and continued beyond the first dose of study treatment, or any medication started on or after the first dose of study treatment up to the last dose of study treatment.

##### **Prior and Concomitant Medications Summaries:**

- Summary of prior medications (Safety Analysis Set, and FAS)
- Summary of concomitant medications (Safety Analysis Set, and FAS)
- Summary of concomitant PD medications (FAS)

##### **Prior and Concomitant Medications Listings:**

- Listing of prior medications
- Listing of concomitant medications

#### **4.7.7. Public Disclosure Requirements**

There are unique summaries required to support reporting on clinicaltrials.gov. For each, the analysis set to use is specified.

##### **Derivations and Definitions:**

For required public disclosure reporting, participants will be categorized into the following age categories:

- In utero
- Preterm newborn (gestational age <37 weeks)
- Newborns (0-27 days)
- Infants and toddlers (28 days – 23 months)
- Children (2-11 years)

- Adolescents (12-17 years)
- Adults (18-64 years)
- Older Adults (65-84 years)
- Oldest Adults (85 years and older)

**Public Disclosure Summaries:**

- Study Disposition by Study Period (for Public Disclosure) using the Full Analysis Set
- Number of Participants Enrolled by Region, Country [and Site] (for Public Disclosure) using the Full Analysis Set
- Number of Participants Enrolled by Age Category (for Public Disclosure) using the Full Analysis Set
- Summary of Treatment-emergent Serious Adverse Events (for Public Disclosure) using the Safety Analysis Set
- Summary of Treatment-emergent Non-serious Adverse Events Occurring in Greater Than 5% of Participants (for Public Disclosure) using the Safety Analysis Set
- Summary of [Grade 5 or Fatal] Treatment-emergent Adverse Events (for Public Disclosure) using the Safety Analysis Set

**4.8. Interim Analyses**

There are no interim analyses currently planned.

#### **4.9. Changes to the Protocol-Planned Analyses**

This SAP added the definition of FAS, defined as “The Full Analysis Set includes all participants who are randomized.” This analysis set will be the primary analysis set for all efficacy analyses.

## 5. SAMPLE SIZE DETERMINATION

A total of 160 participants will be randomized 1:1 to JZP385 or placebo. Participants will be stratified by TETRAS composite outcome score ( $\leq 17$  or  $> 17$ ) as assessed at Baseline.

A sample size of 64 evaluable participants per treatment group will provide 80% power to detect a between-treatment (JZP385 versus placebo) difference of 3.0 points for the change from Baseline to Week 17 on the modified TETRAS composite outcome score, with a common SD of 6.0 points. The TETRAS composite outcome score includes the sum of items 1 to 11 on the TETRAS-ADL subscale and items 6 (6a and 6b) and 7 of the TETRAS-PS. During the analysis, the scores for each item of the TETRAS-ADL subscale will be modified from a 5-point scale (0 to 4) to a 4-point scale by collapsing scores of 0 (normal) and 1 (slight) into 0. Likewise, the scores for the items on the TETRAS-PS will also be modified to a 4-point scale. Thus, across all 14 items of the TETRAS composite outcome score, the highest possible score is 42. Assuming a 20% dropout rate, a total of 160 participants (80 participants per treatment group) will be randomized. All sample size calculations are based on a 2-sided significance level of 0.05 using a 2-sample t-test.

For the key secondary endpoint, the CGI-S score ranges from 1 (no limitations) to 5 (severe limitations). A sample size of 64 evaluable participants per treatment group will also provide adequate power ( $> 80\%$ ) to detect a 25% between-treatment (assuming JZP385 at 65% versus placebo at 40%) difference in proportion of participants who improved by at least 1 point on the CGI-S from Baseline to Week 17.

## 6. SUPPORTING DOCUMENTATION

### 6.1. Incomplete and Missing AE Start Date

The following imputation rules apply for incomplete or completely missing AE start date:

- If *year* is missing (including the situation where the start date is completely missing), set the date to the first dose date.
- If *year* is present, and *month* and *day* are missing, or *year* and *day* are present, and *month* is missing,
  - if *year* = year of first dose, set the date to the first dose date,
  - if *year* < year of first dose, set *month* and *day* to December 31st.
  - if *year* > year of first dose, set *month* and *day* to January 1st.
- If *year* and *month* are present, and *day* is missing,
  - if *year* = year of first dose, and
    - if *month* = month of first dose, set *day* to day of first dose;
    - if *month* < month of first dose, set *day* to the last day of *month*;
    - if *month* > month of first dose, set *day* to the first day of *month*;
  - if *year* < year of first dose, set *day* to the last day of *month*;
  - if *year* > year of first dose, set *day* to the first day of *month*.
- For all other cases that are not covered above, set the date to the first dose date.

Imputed dates for AEs with partial dates will be used to identify treatment emergent AEs and for sorting in data listings. They will not be used to calculate duration of AEs. If an AE start or end date is completely missing, then the duration of the AE will be set to missing and the AE will be considered treatment emergent.

Note that partial or missing AE end dates will not be imputed.

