8.4. Adverse Events, Serious Adverse Events, and Other Safety Reporting

The definitions of AEs and SAEs can be found in [Appendix 4](#).

Adverse events will be reported by the participant (or, when appropriate, by a caregiver, surrogate, or the participant's legally authorized representative).

The investigator and any qualified designees are responsible for detecting, documenting, and recording events that meet the definition of an AE or SAE and remain responsible for following up all AEs (see [Section 8.4.3](#)).

The method of recording, evaluating, and assessing causality of AEs and SAEs and the procedures for completing and transmitting SAE reports are provided in [Appendix 4](#).

8.4.1. Time Period and Frequency for Collecting Adverse Event and Serious Adverse Event Information

All AEs and SAEs will be collected from the start of intervention until the Safety Follow-up Visit at the time points specified in the SoA ([Section 1.3](#)).

Note: All SAEs that occur after the ICF is signed but before study intervention/treatment must be reported by the investigator if they cause the participant to be excluded from the study or if they are the result of a protocol-specified intervention, including but not limited to washout or discontinuation of usual therapy, diet, placebo treatment, or a procedure.

Medical occurrences that begin before the start of study intervention but after obtaining informed consent will be recorded as Medical History/Current Medical Conditions, not as AEs.

All SAEs will be recorded and reported to the sponsor or designee within 24 hours of first knowledge of the event by study personnel, as indicated in [Appendix 4](#). The investigator will submit any updated SAE data to the sponsor within 24 hours of it being available.

Investigators are not obligated to actively seek information on AEs or SAEs after conclusion of the study participation. However, if the investigator learns of any SAE, including a death, at any time after a participant has been discharged from the study, and he/she considers the event to be reasonably related to the study intervention or study participation, the investigator should promptly notify the sponsor.

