#### **Derivations and Definitions:**

AEs will be collected and reported from the start of study treatment up to the Safety Follow-up visit (approximately 14 days after the last dose of study treatment).

A treatment-emergent adverse event (TEAE) is defined as any AE that began on or after the first dose of study treatment until up to 14 days after the last dose of study treatment.

Adverse events of special interest (AESI) are AEs that are of scientific and medical concern specific to JZP385, which includes hallucination, and syncope. The groupings are defined using MedDRA terms, SMQs (standardized MedDRA queries) and PTs.

Time of first onset of AE is calculated as: TEAE start date – First dose date + 1 and is categorized as:

- Week 1 and 2 ( $1 \leq \text{day of first onset of AE} \leq 14$ )
- Week 3 ( $15 \leq \text{day of first onset of AE} \leq 21$ )
- Week 4 ( $22 \leq \text{day of first onset of AE} \leq 28$ )
- Week 5 ( $29 \leq \text{day of first onset of AE} \leq 35$ )
- Weeks 6 – 17 ( $36 \leq \text{day of first onset of AE} \leq 119$ )
- > Week 17 ( $120 \leq \text{day of first onset of AE}$ )

Incomplete AE start/stop date will be imputed according to Section 6.1.

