### 6.3. Incomplete and Missing Prior and Concomitant Medication End Date

The following imputation rules will be followed, when the prior and concomitant medication end date is incomplete (e.g., only *year* is present, but *month* and *day* are missing) or completely missing:

- If it is indicated that the medication is ongoing (i.e., “Yes” is checked for the question “Ongoing?” in the CRF), do not impute, since there should not be an end date for this medication.
- If *year* is missing (including the situation where the end date is completely missing), do not impute, and the end date will be treated as missing in the analysis.
- If *year* is present, and *month* and *day* are missing, or *year* and *day* are present, and *month* is missing, set *month* and *day* to December 31st.
- If *year* and *month* are present, and *day* is missing, set *day* to the last day of *month*.

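### SAP 6.1 makes an AE treatment emergent when only its end date is missing, which overrides a known onset and conflicts with the onset-only TEAE definition in SAP 4.6.2

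*SAP*

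**What the plan says.** SAP 4.6.2 (Derivations and Definitions) defines a TEAE as an "AE that began on or after the first dose of study treatment until up to 14 days after the last dose". The end date plays no part. The same section sends the reader to 6.1 for incomplete start and stop dates.

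SAP 6.1 contains four relevant rules:

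- Its first bullet covers a missing year, "including the situation where the start date is completely missing), set the date to the first dose date".
- Later bullets place some partial start dates before first dose. For example, a start month earlier than the month of first dose becomes the last day of that earlier month.
- "Imputed dates for AEs with partial dates will be used to identify treatment emergent AEs", and "Note that partial or missing AE end dates will not be imputed".
- Between those two statements, it says that if the start date is absent, or if the "end date is completely missing, then the duration of the AE will be set to missing and the AE will be considered treatment emergent".

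For medications, SAP 6.3 separates ongoing from missing: an ongoing item is left alone, "since there should not be an end date for this medication". SAP 6.1 has no counterpart for ongoing AEs.

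Protocol 8.4.1 collects AEs from the start of intervention until the Safety Follow-up Visit and sends most earlier occurrences to medical history. It makes an exception for certain SAEs: "All SAEs that occur after the ICF is signed but before study intervention/treatment must be reported by the investigator" if they lead to exclusion or result from a protocol-specified intervention such as washout.

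**The concern.** Treating an AE of unknown onset as treatment emergent is a sensible inclusive default. Here the default also reaches AEs whose onset is known. An end date carries no information on whether an event began inside the window, so its absence should not change the classification.

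At stake is a consistent TEAE status. Two events with the same known onset outside the window are classified differently according to whether an end date was recorded. The affected event enters the TEAE tables although it does not meet the definition those tables are meant to apply.

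**Working it through.** The plan gives no figure on this point, so the check sets the two rules side by side.

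**Inputs.** L is the study day of last dose. Rule A (SAP 4.6.2): TEAE if onset lies from Day 1 to L + 14. Rule B (SAP 6.1): also TEAE if the start or the end date is completely missing. End dates are not imputed, so a missing one stays missing.

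**Status under A, then under B.**

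| Start date | End date recorded | End date missing |
|---|---|---|
| Completely missing (set to first dose) | yes / yes | yes / yes |
| Before first dose | no / no | no / **yes** |
| Day 1 to L + 14 | yes / yes | yes / yes |
| After L + 14 | no / no | no / **yes** |

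The start half of the 6.1 sentence changes nothing, because the first bullet has already set such an AE to the first dose date. The end half changes status only where the onset lies outside the window, and there it always contradicts 4.6.2. The table shows where the rules disagree. It does not show how often.

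**Illustration, late onset (assumed dates).** Take L = Day 40, so the window ends on Day 40 + 14 = Day 54. An AE starting on Day 55 or Day 61 is not a TEAE if its end date is recorded, and is a TEAE if the end date is missing.

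**How such an AE gets collected.** The Safety Follow-up Visit has to fall after L + 14.

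- Completer: with last dose on Day 119, the window ends on Day 119 + 14 = Day 133. If the +2 day visit window applies to Week 19, which the schedule table as read does not make certain, the visit can be on Day 133 + 2 = Day 135. That is 2 days past the window.
- Early discontinuation: if the visit is held 2 weeks after an early discontinuation visit that itself took place g days after last dose, it falls g days past the window. For assumed g = 0, 3, 7 and 14 that is 0, 3, 7 and 14 days. The documents give no value for g.
- Late notification: Protocol 8.4.1 asks the investigator to tell the sponsor "if the investigator learns of any SAE, including a death, at any time after a participant has been discharged from the study", if reasonably related. The documents do not say whether such an SAE enters the AE dataset.

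**Illustration, pre-dose onset (assumed dates).** Take first dose on 10 June and a reportable washout SAE with start recorded only as May of that year and no end date. SAP 6.1 imputes 31 May. The onset formula in 4.6.2 gives 31 May − 10 June + 1 = −9. Rule A says not a TEAE; rule B says TEAE. The lowest onset category in 4.6.2 starts at day 1, so the event would have no row in the planned time-of-first-onset table.

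**The case against.** The strongest reply is that the two sections are not rivals. SAP 4.6.2 gives the definition and refers to 6.1 for incomplete dates, so one programmer applies both, and an inclusive default is common in safety reporting. The heading of 6.1 concerns start dates, so the end date was probably meant only for the duration clause. The exposed cases are also few by design. AE collection stops at the Safety Follow-up Visit, about 14 days after last dose. Most pre-dose occurrences become medical history, and a participant excluded because of a pre-dose SAE would normally never be dosed and so would be outside the Safety Analysis Set. All AEs are listed whatever their status.

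Most of this stands, and it keeps the point small. The cross-reference does not remove the conflict, however: a programmer who applies both sections faithfully still overrides a known onset. The probable intention is a reason to correct the sentence, since the text as written says something else.

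A reader might infer more than the documents support:

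- *That ongoing AEs in general are misclassified.* They are not. An ongoing AE with onset inside the window is a TEAE under both rules; only one with onset outside it is exposed, and only if ongoing counts as missing.
- *That TEAE incidence is materially inflated, or tilted between arms.* The documents give no rate of late-onset AEs, pre-dose SAEs or missing end dates, in either arm.
- *That pre-dose events will regularly appear in the TEAE tables.* This needs a reportable SAE, in a participant later dosed, held in the AE dataset, with no end date.
- *That the Safety Follow-up timing is part of the same error.* Schedule footnote b counts from the early discontinuation visit and Protocol 7.1.1 from last dose. That is a separate scheduling inconsistency, and re-anchoring it would have its own trade-offs.

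**Conclusion.** The conflict is real on the text: SAP 6.1 classes an AE as treatment emergent because its end date is missing, even where 4.6.2 excludes it on a known onset. It is minor. Only descriptive safety tables are affected, the error can only add events, and no hypothesis test is touched. No event count can be derived.

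The conclusion assumes that the 6.1 sentence is programmed as written. The late-onset case also needs a Safety Follow-up Visit held more than 14 days after last dose. How far ongoing AEs add to it depends on a convention the SAP leaves unstated.

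**What to change.** Split the 6.1 sentence so that the end date governs duration only, for example:

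*Duration is set to missing when either the start date or the end date of an AE is wholly absent. An AE whose start date is wholly absent is considered treatment emergent. In every other case the known or imputed start date determines treatment-emergent status, whatever the end date; this includes ongoing AEs.*

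The two rules then agree in all eight cells of the table. The inclusive default for unknown onset is kept, and the window of last dose + 14 days is unchanged.

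The cost is one reworded SAP rule and the matching line in the TEAE derivation. It needs no new data, no extra visits and no protocol amendment.
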